PUBLISH DATE JUNE 20, 2018

STATISTICAL ANALYSIS PLAN

TITLE: A comparison of early deployment of a video capsule (Endocapsule EC-10: Olympus Tokyo. Japan) in the Emergency Department versus conventional work-up of non-hematemesis gastrointestinal bleeding [NHGIB].

NCT02442830

[name], PHD, PRINCIPAL INVESTIGATOR

STATISTICAL ANALYSIS PLAN

Study outcomes:

The primary outcome for this study was the rate of localization of bleeding during hospitalization. Localization of bleeding was defined as identification of blood or identification of a lesion with high-risk stigmata of recent hemorrhage (SRH). Secondary outcomes included, overall rate of localization of bleeding by the end of admission, anatomic location of bleeding or the bleeding source, rate of endoscopic therapy, rate of readmission, rate of diagnosis of vascular lesions (defined as Dieulafoy's lesions or angioectasias), rate of re-bleeding within 30 days of discharge, rate of all-cause mortality within 30 days of hospitalization, cumulative direct hospital costs by the end of admission, and overall rate of identifying the etiologic diagnosis.

Sample size calculation:

The study was planned as a superiority trial and the estimated probability of localization of bleeding during hospitalization in the Early Capsule arm to be two times greater than that of the Standard of Care arm (i.e. estimated hazard ratio of 2.00). We found no prior studies similar to our methodology, so prior experience at our institution guided the estimation of effect. Power analysis revealed that for this effect size to be detected (80% chance) as significant at the 5% level, a sample of at least 72 patients (36 per group) would be required.

Statistical analysis:

Patient characteristics were described as means with standard deviation (SD) or as proportions. Time to localization and time to first procedure were described using medians with interquartile range (IQR). Hospital costs were described in US dollars (USD).

Independent variables selected for analysis included those previously suggested as prognostic indices for NHGIB. Variables chosen for analysis included gender, race, age, vital signs at admission, use of anticoagulants, use of non-steroidal anti-inflammatory drugs (e.g. aspirin and ibuprofen; NSAIDs), use of a P2Y₁₂ inhibitor (e.g. clopidogrel), factors that contribute to the Glasgow-Blatchford Score, and type of bleeding at admission (i.e. hematochezia, melena, or symptomatic anemia).

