Univariate analyses involved Wilcoxon-Rank sum tests for continuous variables and Chi-square or Fisher's Exact tests for binary variables. A Kaplan-Meier survival analysis with a Log-rank test compared the cumulative incidence of endoscopic localization of bleeding for the two groups. For multivariate analyses, independent variables with a difference at $p<0.10$ following univariate analysis or those noted to be unevenly distributed between the two cohorts were included as covariates. A p -value of less than 0.05 was significant. Statistical analysis was performed using STATA 13.

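### Covariates for the adjusted analysis are picked from the trial data by p<0.10 or noticed imbalance, so the adjusted treatment effect depends on chance hits and analyst discretion; a short list fixed on clinical grounds would be a cheap improvement.

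*SAP*

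**What the plan says.** The Statistical analysis section of the SAP starts from a pool of candidates chosen for their prognostic interest: "Independent variables selected for analysis included those previously suggested as prognostic indices for NHGIB". It then names them, beginning "Variables chosen for analysis included gender, race, age, vital signs at admission, use of anticoagulants" and continuing through NSAIDs, P2Y12 inhibitors, the Glasgow-Blatchford components and bleeding type at admission. That is at least nine items or groups, and more once vital signs and the Glasgow-Blatchford components are counted separately.

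The pool is not the adjustment set. The screening tests are given as "Univariate analyses involved Wilcoxon-Rank sum tests for continuous variables and Chi-square or Fisher's Exact tests for binary variables". Variables that differ at p<0.10 on univariate analysis enter the multivariate model, and "those noted to be unevenly distributed between the two cohorts were included as covariates".

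Four things are not stated:

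- whether the p<0.10 difference is between arms or by outcome
- what counts as uneven
- which multivariate model is fitted, and to which outcome
- how the adjusted result ranks against the unadjusted one

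The only named test comparing the arms on localization is unadjusted: "A Kaplan-Meier survival analysis with a Log-rank test compared the cumulative incidence of endoscopic localization of bleeding for the two groups". The data analysis plan in Protocol section 12 has chi-square tests, t-tests and Kaplan-Meier curves, and no adjusted model.

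**The concern.** Patients are randomised (Protocol section 10), so a baseline difference between arms says nothing about whether a variable predicts localization. Screening on that difference admits noise variables and leaves out strong predictors that happen to be balanced. Because the imbalance clause has no threshold, two analysts following this SAP could fit different models to the same data. Nothing requires the choice to be made before the treatment effect is seen.

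At stake are the adjusted estimate, its interval and its p-value. Covariate adjustment is worth having because it can add precision, and a rule that selects on imbalance may give that up. The reader also gets two treatment p-values, log-rank and adjusted, with no stated order between them.

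**Working it through.** **1. The plan's own figure.** The inputs from the SAP's Sample size calculation section are "estimated hazard ratio of 2.00", and an effect to be "detected (80% chance) as significant at the 5% level", with 36 per group. Sidedness is not given; two-sided is assumed. Freedman's formula gives

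events = (1.960 + 0.842)² × [(2 + 1)/(2 − 1)]² = 7.849 × 9 = 70.6, so 71, or 72 at 36 per arm.

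This reproduces the stated 72 if every patient has an event. (Schoenfeld's formula gives 4 × 7.849/(ln 2)² = 65.3, so 66.) The calculation contains no covariates, so the selection rule does not touch it.

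**2. Chance hits.** For k independent candidates unrelated to arm, screened at 0.10, the expected number admitted is 0.10k and the chance of at least one is 1 − 0.9^k. The range k = 9 to 20 is an assumption, since the SAP's groups can be expanded in different ways.

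| k | Expected hits | At least one |
|---|---|---|
| 9 | 0.9 | 61% |
| 16 | 1.6 | 81% |
| 20 | 2.0 | 88% |

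Under a between-arm screen the same 10% applies to a real predictor. With three independent predictors, all three are left out with probability 0.9³ = 0.73.

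**3. Power for the treatment effect.** Assumed inputs: 72 patients, 1:1, about 45 events, 15 independent candidates of which 3 are prognostic (log hazard ratio 0.5 each), treatment hazard ratio 2, Cox model with Wald test. A between-arm p<0.10 stands in for the clause that has no threshold. Ranges are across repeat runs.

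| Model | Power |
|---|---|
| Unadjusted | about 41% |
| SAP rule, screen between arms only | about 41% |
| SAP rule, screen by arm or outcome | about 49% (47-52%) |
| Fixed list of three, all prognostic | about 59% (59-60%) |
| Fixed list, two of three prognostic | about 52% (50-53%) |
| Fixed list, one of three prognostic | about 46% (45-48%) |
| Fixed list, none prognostic | 39-41% |

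Type I error was about 4-7% for these models.

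**4. A second set of assumptions.** Here there were 9 or 16 candidates, 4 of them prognostic (log hazard ratio 0.3 or 0.5 per SD), with all patients or 60% localized.

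- Screening by arm or outcome: 69-72% power against 77-79% for the fixed prognostic list (all localized), and 51-53% against 58-61% (60% localized). Size-adjusted power still favoured the fixed list by about 4-10 points.
- Screening by arm only: 44-64% (all localized) and 36-49% (60% localized), a loss of about 11-35 points against the fixed list.
- With either screen, at least one pure-noise covariate entered in 66-67% of trials (9 candidates) or 93-94% (16 candidates). The significance verdict differed from the fixed-list model in about 9-13% of trials.
- Under the arm-only screen with 16 candidates and all localized, the median adjusted hazard ratio was 1.60-1.80, against 2.07-2.09 for the fixed list and a true conditional value of 2.00. A hazard ratio changes meaning with the prognostic covariates in the model, so a data-driven set also leaves open what is being estimated.
- A list with only two of four variables prognostic did worse than outcome screening at log hazard ratio 0.5 (57-60% against 70-71%, all localized). Forcing in all 16 candidates raised type I error to about 9-12% with no size-adjusted gain (64% against 68%).

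**The case against.** The strongest objection is that 59% belongs to a list an oracle would write. No document says which candidates predict localization, or how strongly. If the p<0.10 screen includes outcome, one wrong choice in three brings the fixed list to about the same power as the SAP rule (52% against 49%, with overlapping ranges), and two wrong choices leave no gain over it (46%). This stands, and it makes the power argument conditional. If the screen is between arms only, the rule gains nothing and a fixed list is at least as good.

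A reader might infer that the rule inflates false positives. The simulations do not support that: type I error is near nominal for the rule and for the short fixed list alike. A rate of about 10% appears only if someone reports whichever of the unadjusted and selected models is significant. The SAP does not provide for that, and deleting the covariate rule would not by itself prevent it.

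It may also be said that imbalance here is not always chance. Protocol section 14 removes patients who cannot swallow the capsule, and section 10 gives a capsule to all early-capsule patients but only some conventional ones, so exclusions could differ by arm. That is a fair limit on any claim that imbalance is pure chance. It does not rescue a clause with no threshold.

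Finally, the SAP is dated June 2018 and written in the past tense. If the analysis had been run, a list named now is not pre-specified. This also stands, and the fix allows for it.

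**Conclusion.** The point holds as a defect of the adjusted analysis. Covariates are chosen from the trial data, one entry route has no threshold, the other does not say what is compared with what, and neither document repairs this. Selection on between-arm imbalance gives essentially no precision gain over no adjustment. Selection by arm or outcome recovers about 8 of a possible 18 points (41% to 49%, against 59%) under the assumptions of step 3.

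A reader might conclude that the trial's power or its main comparison is compromised. The documents do not support that: the log-rank test uses no covariates, and the 72-patient figure reproduces without them. Nor can a fixed list be promised to beat the rule, since that depends on how well it is chosen. The sizes rest on assumed prognostic strengths, candidate counts, event numbers and a Cox model, none of which the SAP gives, and they move by several points as these change.

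Confidence is medium. This is a cheap improvement to what should be a supportive analysis. It would matter more if the adjusted estimate were the one reported as the result, which the SAP leaves open.

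**What to change.** Delete both selection rules. Name a short list on clinical grounds from variables the SAP already gives, for example Glasgow-Blatchford score (from its listed components), age and type of bleeding. Fit it in a Cox model for localization whatever the observed imbalance. Do not force in the whole pool. State that the log-rank test is primary and the fixed-covariate model supportive.

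If the analysis has already been run, report which covariates entered and why, label that model as data-driven, and show it beside the unadjusted and fixed-list results. A list written at that stage should be described as chosen afterwards.

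The cost is mainly wording. Confirm that the listed variables were collected, because the data list under Review and Follow-Up in Protocol section 10 does not name anticoagulants or the Glasgow-Blatchford components (section 12 adds laboratory values and further measures). The downsides are that the gain depends on the listed variables being prognostic, and that the list cannot react to a chance imbalance in a variable left off it.
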